### Summary of Revisions

Version #	Description	Date
11-005-01	Original version	12 December 2012
11-005-02	Provision for retrospective enrollment	13 March 2013
11-005-03	Sponsor change	04 Apr 2018

---

**Zenith® Fenestrated AAA Endovascular Graft Long-Term Study (P020018/S44)****1.0 Clinical Investigation Plan Overview**

The purpose of this post-approval study is to evaluate the long-term safety and performance of the Zenith® Fenestrated AAA Endovascular Graft to treat aortic or aortoiliac aneurysms in patients with short aortic infrarenal necks by evaluating primarily aneurysm-related mortality.

This study will enroll 88 total patients (including patients enrolled in the pivotal and continued/expanded access phases of the pre-approval study) with 21 new patients to be enrolled (prospectively or retrospectively) from a minimum of 5 sites that will be randomly selected from the pool of institutions that use the standard (non-fenestrated) Zenith AAA Endovascular Graft, did not enroll in the pre-approval study, have completed the commercial training program, and have the necessary research infrastructure and staff to support the study, thus providing for a secondary assessment of commercial training program effectiveness.

Patients with anatomy amenable to endovascular repair and meet other enrollment criteria will be included in the study. Patients who do not meet the criteria will be excluded. A patient will be considered enrolled in the study once the delivery system of the study device has been inserted under the skin.

At the physician's discretion, the Zenith® Alignment Stent may be used to stent visceral vessels targeted by a fenestration. Clinical and imaging follow-up will be performed in accordance with standard of care through 5 years. The primary endpoint is aneurysm-related mortality; additional endpoints to be assessed include morbidity, device integrity, device patency, change in aneurysm size, endoleak, migration, conversion, rupture, and secondary interventions.

**2.0 Product Description and Intended Use****2.1 General Product Description**

The Zenith® Fenestrated AAA Endovascular Graft is a modular system consisting of three components, a proximal body graft, a distal bifurcated body graft and one iliac leg. Additional ancillary components (main body extensions, iliac leg extensions, converters, and occluders) are available. The Zenith® Alignment Stent is a balloon-expandable stent that can be deployed through scallops or fenestrations in a Zenith® Fenestrated AAA Endovascular Graft into branch vessels of the aorta.

A more complete product description, discussion of the principle of operation, installation, storage and handling requirements, preparation for use and any intended re-use, pre-use checks for safety and performance, precautions to be taken after use, summary of necessary training and experience, description of procedures required for use, and results from previous clinical experience with the Zenith® Fenestrated AAA Endovascular Graft and Zenith® Alignment Stent, are found in their respective Instructions for Use (IFU).

**Zenith® Fenestrated AAA Endovascular Graft Long-Term Study (P020018/S44)****2.2 Intended Use**

The Zenith® Fenestrated AAA Endovascular Graft with the H&L-B One-Shot™ Introduction System is indicated for the endovascular treatment of patients with abdominal aortic or aortoiliac aneurysms having morphology suitable for endovascular repair including:

- Adequate iliac/femoral access compatible with the required introduction systems.
- Non-aneurysmal infrarenal aortic segment (neck) proximal to the aneurysm:
  - with a length of at least 4 mm and unsuitable for a non-fenestrated endograft,
  - with a diameter measured outer wall to outer wall of no greater than 31 mm and no less than 19 mm,
  - with an angle less than 45 degrees relative to the long axis of the aneurysm, and
  - with an angle less than 45 degrees relative to the axis of the suprarenal aorta.
- Ipsilateral iliac artery distal fixation site greater than 30 mm in length and 9-21 mm in diameter (measured outer wall to outer wall).
- Contralateral iliac artery distal fixation site greater than 30 mm in length and 7-21 mm in diameter (measured outer wall to outer wall).

The Zenith® Alignment Stent is indicated for use as an adjunct to the Zenith® Fenestrated AAA Endovascular Graft to assist alignment and patency at the orifice of aortic branch vessels with diameters ranging from 3 to 8 mm.

**3.0 Objectives of the Clinical Investigation**

The purpose of the study is to evaluate the long-term safety and performance of the Zenith® Fenestrated AAA Endovascular Graft to treat aortic or aorto-iliac aneurysms in patients with short aortic infrarenal necks in the US.

**3.1 Primary Objectives**

The primary objectives of the study is to assess the long-term safety and performance of the Zenith® Fenestrated AAA Endovascular Graft and determine if the 5-year aneurysm-related mortality is reasonable considering the treatment alternatives.

**3.2 Secondary Objectives**

The secondary objectives of the study are to:

- perform additional assessments of rupture, conversion, morbidity, device integrity, device patency, change in aneurysm size, endoleak, migration, and secondary interventions.
- evaluate commercial training program effectiveness as measured by the composite freedom from the following events at 30 days in up to 3 patients from each site: technical failure, loss of patency (by core lab analysis), rupture, secondary intervention, conversion, Type I or III endoleak (by core lab analysis). Results for patients enrolled by physicians that completed the commercial training

**Zenith® Fenestrated AAA Endovascular Graft Long-Term Study (P020018/S44)**

program (i.e., un-proctored cases) will be compared to results for patients treated by physicians that did not complete the training program (i.e., physicians that enrolled patients in the pre-approval study).

3.3 Specific Hypothesis to be Accepted or Rejected by Statistical Data  
Long-term safety and performance of the Zenith® Fenestrated AAA Endovascular Graft will be evaluated by testing a primary hypothesis related to the rate of AAA-related mortality.

The primary endpoint will be evaluated according to the hypothesis that patients treated with the Zenith® Fenestrated AAA Endovascular Graft will have a rate of aneurysm-related mortality at 5 years that meets a performance goal of 18% (see Section 6.0), and is expressed as follows:

*Null Hypothesis:* the 5-year AAA-related mortality rate,  $\gamma$ , is greater than or equal to 18%. (Interpretation: the AAA-related mortality rate does not meet the performance goal.)

$H_0: \gamma \geq 18\%$

*Alternative Hypothesis:* the 5-year AAA-related mortality rate,  $\gamma$ , is less than 18%. (Interpretation: the AAA-related mortality rate does meet the performance goal.)

$H_a: \gamma < 18\%$

Same as the agreed upon post-approval study for P070016, which similarly had a 5-year aneurysm-related mortality endpoint, the hypothesis for this study will be tested by using an exact binomial test where the test statistic is defined as follows:

$$\hat{\gamma} = \frac{n_{AAA}}{N}$$

where  $n_{AAA}$  is the number of patients with AAA-related death within 5 years, and  $N$  is the total number of patients with 5-year follow-up or death (any cause) within 5 years.

Per FDA request, the primary endpoint will also be assessed through Kaplan-Meier analysis. For this purpose, the primary endpoint (expressed in terms of freedom from aneurysm-related mortality) will be assessed using a Z-statistic against the performance goal of 82%. The Z-statistic is given by:

$$Z = (ARM_{FEN} - 0.82)/SE$$

where

$ARM_{FEN}$  = Kaplan-Meier estimated freedom from AAA-related mortality at 5 years post-procedure.

$SE$  = Standard Error =  $\sqrt{V(ARM_{FEN})}$

where  $V(ARM_{FEN})$  is the estimate of the variance of the Kaplan-Meier estimate

**4.0 Design of the Clinical Investigation****4.1 Type of Investigation**

This is a non-randomized, multi-center cohort study consisting of a combination of extended follow-up of subjects included in the pre-approval study (n=67) and newly enrolled subjects (21 patients from a minimum of 5 sites), providing a total enrollment of 88 patients. The newly enrolled patients (to be enrolled either prospectively or retrospectively) will be from centers that were randomly selected from the pool of institutions that use the standard (non-fenestrated) Zenith AAA Endovascular Graft, did not enroll in the pre-approval study, have completed the commercial training program, and have the necessary research infrastructure and staff to support the study. All patients, if found to be eligible for study participation, will be invited to participate in the study. All patients that meet the inclusion criteria/exclusion criteria at participating sites and who are willing to provide consent will be enrolled.

**4.2 Endpoints**

The primary endpoint of the study is to assess the long-term safety of the Zenith® Fenestrated AAA Endovascular Graft as measured by aneurysm-related mortality (AAA-related mortality) through 5 years.

The secondary endpoints of the study are to:

- perform additional assessments of rupture, conversion, morbidity, device integrity, device patency, change in aneurysm size, endoleak, migration, and secondary interventions.
- evaluate training program effectiveness as measured by the composite freedom from the following events at 30 days in up to the first 3 patients from each site: technical failure, loss of patency (by core lab analysis), rupture, secondary intervention, conversion; Type I or III endoleak (by core lab analysis).

**4.3 Variables to be Measured to Demonstrate Achievement of Endpoints**

To evaluate AAA-related mortality, information regarding each patient death (e.g., date of death, cause of death) will be captured on the applicable case report form.

Secondary objectives will be evaluated through the following:

- Complications (e.g., those comprising the morbidity index) and secondary interventions, if any, will be captured throughout the course of the study on

**Zenith® Fenestrated AAA Endovascular Graft Long-Term Study (P020018/S44)**

- applicable case report forms.
- Assessment of device outcome (e.g., integrity, patency, aneurysm size, endoleak, and migration) will be captured from available intra-operative and follow-up imaging.

**4.4 Inclusion Criteria**

Patients must meet at least one of the inclusion criteria below to be enrolled in the study. General and medical exclusion criteria will be assessed during the initial patient evaluation by collecting medical history and performing a physical examination. Anatomical exclusion criteria will be assessed using a variety of imaging techniques that are routinely performed during the evaluation of abdominal aortic aneurysms. Sectional imaging will be performed by CT scan. Angiography and intravascular ultrasound will be performed selectively.

Assessment of entry criteria will be based upon data available prior to enrollment. Data obtained peri-operatively and post-operatively may contradict pre-enrollment assessment, and is anticipated in several cases. However, such contradiction should not be construed as evidence of inadequate or inaccurate pre-enrollment assessment with respect to the enrollment criteria or evidence of inappropriate enrollment. Enrollment is to be based upon best available pre-enrollment data. Therefore, some criteria relate to subjective assessment while other criteria are considered absolute and able to be determined definitively. Variability in assessment between centers, investigators and observers is expected with several criteria.

*Inclusion Criteria:*

A patient may be suitable for inclusion in the study if the patient has at least one of the following (and in the opinion of the investigator, is not a good candidate for open surgical repair and also does not have proximal neck anatomy suitable for treatment with a non-fenestrated graft):

- 1) Aortic or aortoiliac aneurysm with diameter  $\geq 5$  cm
- 2) Aortic or aortoiliac aneurysm with a history of growth  $\geq 0.5$  cm per year, or clinical indication for AAA repair

*Exclusion Criteria:*

Patients must be excluded from the study if any of the following conditions are true:

**General Exclusion Criteria**

- 1) Less than 18 years of age
- 2) Life expectancy less than 2 years
- 3) Pregnant or breastfeeding
- 4) Unwilling to comply with the follow-up schedule
- 5) Inability or refusal to give informed consent

**Medical Exclusion Criteria**

**Zenith® Fenestrated AAA Endovascular Graft Long-Term Study (P020018/S44)**

- 1) Baseline creatinine > 2.0 mg/dl
- 2) Cultural objection to receipt of blood or blood products
- 3) Allergy to stainless steel, polyester, solder, gold, or nitinol
- 4) Anaphylactic reaction to contrast that cannot be adequately pre-medicated
- 5) Leaking/ruptured or symptomatic aneurysm
- 6) Uncorrectable coagulopathy
- 7) Previous stent at the ostium of any renal or visceral artery to be accommodated with a small fenestration

**Anatomical Exclusion Criteria**

- 1) Prohibitive occlusive disease, tortuosity, or calcification of intended access vessels
- 2) Prohibitive occlusive disease, tortuosity, or calcification of intended fixation sites
- 3) Proximal neck < 4 mm, or  $\geq 15$  mm in length unless otherwise compromised to preclude seal
- 4) Proximal neck, measured outer wall to outer wall on a sectional image (CT), > 31 mm in diameter or < 19 mm in diameter
- 5) Proximal neck angulated more than 45 degrees relative to the long axis of the aneurysm
- 6) Immediate suprarenal neck angulated more than 45 degrees relative to the immediate infrarenal neck
- 7) Proximal neck diameter change over the length of the proximal seal zone  $\geq 4$  mm
- 8) Proximal seal site with circumferential thrombus/atheroma above the renal arteries
- 9) Tortuosity, calcification, or arterial diameter, measured inner wall to inner wall on a sectional image (CT), that is not conducive to placement of the 20 Fr introducer sheath
- 10) Ipsilateral iliac artery fixation site diameter, measured outer wall to outer wall on a sectional image (CT), < 9.0 mm (prior to deployment) unless an additional iliac leg graft is to be deployed
- 11) Iliac artery diameter, measured outer wall to outer wall on a sectional image (CT), < 7.0 mm or > 21 mm at distal fixation site
- 12) Iliac artery distal fixation site < 30 mm in length
- 13) Inability to maintain at least one patent hypogastric artery
- 14) Renal artery stenosis > 50% (prior to deployment)
- 15) Non-bifurcated segment of any artery to be stented < 15 mm in length, unless an uncovered stent is intended to be deployed.
- 16) Artery to be stented with a maximum diameter < 3 mm or > 8 mm at the vessel ostium
- 17) Unsuitable arterial anatomy

**4.5 Point of Enrollment**

**Zenith® Fenestrated AAA Endovascular Graft Long-Term Study (P020018/S44)**

Point of enrollment will be based on the intent-to-treat population, and is defined to include any patient for which informed consent has been obtained and the treatment procedure is initiated. More specifically, once the delivery system of the study device (Zenith® Fenestrated AAA Endovascular Graft) has been inserted under the patient's skin, this patient would be included in the intent-to-treat population. Primary statistical analyses will be based on this set of patients.

**4.6 Enrollment Objective and Study Timeline**

The training requirements, anticipated rate of enrollment (based on that from the pre-approval study, which averaged 0.79 patients/site/year during the final year prior to approval), and length of follow-up dictate the overall timeline for the study. Each physician will first need to complete the training program and case proctoring before becoming eligible to enroll cases in the post-approval study. Based on this, and given that at least 5 sites will participate in this long-term study, a training period (including proctoring) and study start-up period (with IRB review, which cannot initiate until the protocol is formally approved by FDA) of approximately 1.25 years (beginning in June 2012) is anticipated prior to the sites being eligible to enroll (by September 2013), following which it is estimated to take approximately 5 years to complete enrollment of 21 new patients (for an approximate enrollment completion date of September 2018). Follow-up data will continue to be collected for 5 years after graft deployment (completing by September 2023), with a final report projected to be submitted approximately 3 months after patient follow-up is completed (December 2023).

**5.0 Methods**

For information related to endovascular graft planning and sizing, choosing and measuring proximal and distal fixation sites, determining anatomical lengths, endovascular graft and fenestration stent placement procedures, follow-up care, and treatment of endoleaks, please refer to the device IFU.

Informed consent will allow for follow-up data to be collected according to standard of care for five years after graft deployment for each patient in the study.

**5.1 Measurements and Data Collection**

Clinical data and imaging measurements will be collected on standardized forms. Clinical and imaging follow-up will be performed in accordance with standard of care at each institution through 5 years. An example of the expected standard of care follow-up for the Zenith® Fenestrated AAA Endovascular Graft is provided in the table below (Table 5.1-1).

Zenith® Fenestrated AAA Endovascular Graft Long-Term Study (P020018/S44)

Table 5.1-1. Expected standard of care follow-up schedule

Example of Expected Follow-up Schedule					
	Pre-procedure	Procedure	30 Day	6 Month (optional)	12 Month 
Clinical exam	X		X	X	X
CT	X		X 	X 	X 
Device x-ray			X	X	X
Angiography	X 	X			
Renal duplex ultrasound	X		X	X	X
Blood tests to assess renal function (e.g., serum creatinine, BUN)	X		X	X	X
 Duplex ultrasound along with a non-contrast CT may be used to assess the aneurysm for those patients experiencing renal failure or who are otherwise unable to undergo contrast enhanced CT scan.  Pre-procedure angiography may be required at the discretion of the implanting physician or film reviewer.  Patients will be followed at yearly intervals through five years.					

5.2 Subject Consent

Patients who meet the inclusion/exclusion criteria will be invited to participate in this investigation. All patients eligible for entry into the investigation will have the clinical investigation plan explained to them, as well as potential risks and benefits of their participation in the investigation. Each patient who agrees to participate will be required to sign an informed consent document prior to his or her enrollment into the study.

5.3 Pre-procedure

Detailed pre-procedural examination data will be collected for patients meeting the selection criteria who have provided informed consent. Information collected will include a patient history as well as anatomical information from available imaging.

5.4 Procedure

The endovascular aneurysm procedure will be documented in such a way to permit analysis of any untoward occurrences in terms of cause and effect. Data will be collected and stored in a database. Data collected will include the number of arteries stented and the types of stents used.

**Zenith® Fenestrated AAA Endovascular Graft Long-Term Study (P020018/S44)**

### 5.5 Follow-up

The results of the endovascular repair will be assessed by radiologic and/or clinical criteria in accordance with standard of care through 5 years. An example of the expected standard of care for patients implanted with the Zenith® Fenestrated AAA Endovascular Graft is described in Table 5.1-1. Data collected will include the results of available clinical and imaging assessments as well as the available details of any deaths, conversions, ruptures, adverse events, explants, or cases of patients who are lost to follow-up or withdraw from the study.

Information on clinical outcomes is expected to be collected annually through 5 years post-procedure on at least 80% of patients enrolled (excluding those discontinued due to death).

To ensure maximum follow-up, each patient's nominal anniversary date for follow-up will be calculated upon enrollment and provided to both the patient and the site. Sites will be notified if follow-up data have not been received for patients who are eligible, and sites will be expected to attempt to contact a patient for follow-up via telephone, mail, and through the last known contact for the patient. Only when each attempt has been unsuccessful should a patient be considered lost to follow-up (LTF). The investigator is also expected to remind the patient about the importance of adhering to the study follow-up schedule.

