**6.2 Sample Size Calculation**

Evaluation of the primary hypothesis, 5-year AAA-related mortality rate, requires 70 patients to determine if the performance goal of 18% has been met. Cook will enroll a total of 88 patients, allowing for an additional 14% for patients who may withdraw or be lost to follow-up (based on the rate from the pre-approval study) plus 6 additional patients to compensate for a one-time loss of 6 patients who refused to consent for long-term follow-up in the pre-approval study.

Sample size calculation for the primary hypothesis can be performed with the following assumptions. Using a performance goal of 18%, an expected mortality rate of 8%, a one-sided test with exact binomial calculation, a type I error rate of 0.05 and power of 0.8, 70 patients are required to demonstrate that the Zenith® Fenestrated AAA Endovascular Graft meets the stated performance goal. The calculation was performed with the SAS UnifyPow macro.

Information on clinical outcomes is expected to be collected annually through 5 years post-procedure on at least 80% of patients enrolled (excluding those discontinued due to death).

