**9.4 Criteria and Procedures for Withdrawal**

The reasons for withdrawal and discontinuation of any patient from the investigation shall be recorded. If such discontinuation is because of problems with safety or lack of effectiveness, that patient shall still be followed in the investigation, if possible.

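### A patient can be classed as lost after three failed contact routes with no check of death or hospital records, so an aneurysm-related death away from the site can go uncounted in the primary endpoint

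*Protocol*

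**What the plan says.** Protocol section 5.5 (Follow-up) sets the tracing rule. When data are overdue, "sites will be expected to attempt to contact a patient for follow-up via telephone, mail, and through the last known contact for the patient". A patient is to be considered lost only after every one of these attempts has failed. No further step is listed, and no other section asks for a search of death records or of records at other hospitals.

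Section 9.4 covers patients who leave the study: "If such discontinuation is because of problems with safety or lack of effectiveness, that patient shall still be followed in the investigation, if possible". It makes no such provision for patients who discontinue for other reasons.

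Section 3.3 defines the denominator of the primary exact binomial test: N "is the total number of patients with 5-year follow-up or death (any cause) within 5 years". In the Kaplan-Meier analysis requested by FDA, patients are censored at withdrawal or loss to follow-up.

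Section 6.2 expects some loss, "allowing for an additional 14% for patients who may withdraw or be lost to follow-up", and adds further enrolment, "plus 6 additional patients to compensate for a one-time loss of 6 patients who refused to consent". Appendix C counts death from rupture through 5 years as aneurysm-related mortality.

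**The concern.** A death at another hospital or at home is itself a reason why a patient cannot be reached. If the telephone, mail and last-known-contact attempts all fail, the patient is recorded as lost and not as dead. An aneurysm-related death of this kind leaves both the numerator and the denominator of the binomial rate, and in the Kaplan-Meier analysis it becomes a censoring time instead of an event.

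This is a matter of finding deaths, which the protocol itself fixes as a site procedure. Sections 4.3, 8.2 and 8.3 say how a known death is recorded, adjudicated and reported; they do not say how an unknown one is found. An analysis rule can explore the uncertainty afterwards, but it cannot supply a death that nobody looked for. At stake is a single-arm mortality claim against a fixed goal, where one or two events near the limit can decide the result.

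**Working it through.** **Inputs.** Section 6.2: "Using a performance goal of 18%, an expected mortality rate of 8%, a one-sided test with exact binomial calculation", and "a type I error rate of 0.05 and power of 0.8, 70 patients are required". The same section gives the 14% allowance for withdrawal and loss, the 6 extra patients and the total of 88.

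**1. The plan's own figures.** The test passes with c deaths among n patients if P(X ≤ c | n, 0.18) ≤ 0.05.
- n = 70: P(X ≤ 7) = 0.0492 and P(X ≤ 8) = 0.096, so the highest passing count is 7. Power at 8% is P(X ≤ 7 | 70, 0.08) = 0.8046.
- Enrolment: 70/0.86 = 81.4, rounded up to 82; 82 + 6 = 88.
- Expected withdrawn or lost: 82 − 70 = 12.

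The sample size reproduces and is not in error.

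**2. Effect of deaths found among the 12 (assumed counts).**

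| Observed | Found | Only the found deaths added back | All 12 resolved |
|---|---|---|---|
| 7/70, p = 0.049, met | 1 | 8/71, p = 0.088, missed | 8/82, p = 0.029, met |
| 7/70, p = 0.049, met | 2 | 9/72, p = 0.143, missed | 9/82, p = 0.059, missed |
| 6/70, p = 0.022, met | 1 | 7/71, p = 0.044, met | 7/82, p = 0.013, met |
| 6/70, p = 0.022, met | 2 | 8/72, p = 0.080, missed | 8/82, p = 0.029, met |
| 6/70, p = 0.022, met | 3 | 9/73, p = 0.132, missed | 9/82, p = 0.059, missed |

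The second starting point is close to the planned rate, since 0.08 × 70 = 5.6. The right-hand column is the fair comparison for a record check, because such a check also confirms survivors.

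**3. Chance of a false pass.** Let the true rate be 18%, total loss 14%, and f the share of all aneurysm-related deaths that fall among the lost. The rate among retained patients is r = 0.18(1 − f)/0.86, and the aneurysm-death share among the lost is 0.18f/0.14. The false-pass rate is P(X ≤ 7 | 70, r).

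| f (assumed) | Share among the lost | r | False-pass rate |
|---|---|---|---|
| 10% | 12.9% | 0.188 | 3.4% |
| 14% | 18.0% | 0.180 | 4.9% |
| 15% | 19.3% | 0.178 | 5.4% |
| 20% | 25.7% | 0.167 | 8.2% |
| 25% | 32.1% | 0.157 | 12.3% |

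The break-even point is f = 14%, where the lost die of the aneurysm as often as everyone else. Below it the test is conservative; above it the type I error exceeds the nominal level.

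**The case against.** The strongest reply is that loss alone does not bias the rate. The binomial denominator keeps every known death but drops survivors who lack 5-year follow-up, which pushes the observed rate up. The net direction therefore depends on who is lost, and the documents give no evidence that aneurysm-related deaths are over-represented. This stands, and it makes the bias conditional. It does not remove the gap, because without a record check nobody can tell which case applies.

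Four stronger readings are tempting, and the documents do not support them.

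- *A reader might infer that deaths reach the study only through these contacts.* Deaths also arrive on case report forms (4.3), on Event forms (8.3) and through the Data Coordinating Center's regular data review (8.2), and a last known contact may report one. The gap is a death away from the site that none of these routes brings in.
- *A reader might compute larger false-pass rates by removing only aneurysm-related deaths.* With r = 0.18(1 − f)/(1 − 0.18f), the results for f = 10%, 15% and 20% are 9.1%, 12.1% and 16.0%. That treats every lost patient as an aneurysm-related death, which contradicts the plan's 14% total loss.
- *A reader might set 12 expected losses against 7 deaths as if 7 were the margin.* Seven is the highest passing count at n = 70, not a distance from failure. The 12 also include withdrawals, which do not arise from failed contact.
- *A reader might infer that consent bars confirming year-5 status after the anniversary.* Section 5.0 says "Informed consent will allow for follow-up data to be collected according to standard of care for five years after graft deployment", which describes a data period and does not expressly forbid later confirmation. The consent pages are not available, so this cannot be judged.

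Finally, tracing detail may sit in site or monitoring procedures that are not shown. But section 5.5 itself states when a patient may be called lost, and that is the rule to amend.

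**Conclusion.** The point holds as a gap in ascertainment, with a conditional effect on the primary result. Section 5.5 allows loss to be declared without a records check, section 9.4 does not extend continued follow-up to every withdrawal, and section 3.3 then leaves such patients uncounted. The primary rate is too low if aneurysm-related deaths are over-represented among the roughly 12 patients expected to withdraw or be lost.

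At the passing limit of 7/70, with all 12 resolved, one found death leaves the goal met and two reverse it. Near the planned rate, at 6/70, it takes three. The type I error stays at or below 4.9% while no more than 14% of aneurysm-related deaths are among the lost, and reaches 8.2% at 20% and 12.3% at 25%. These shares are assumptions, since the documents give no figure for them. The calculations also assume that exactly 70 patients are evaluable. This is a worthwhile, inexpensive improvement; it does not show that the planned result would be wrong.

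**What to change.** - **Section 5.5:** before a patient is classed as lost, require a vital-status and cause-of-death check in death records and in the records of referring or treating hospitals. Repeat it once at study close for every lost or withdrawn patient whose consent allows it.
- **Counting:** state that patients confirmed alive at 5 years enter the primary denominator, as deaths found do. Adding back only the deaths would bias the rate upward.
- **Section 9.4:** offer record-only vital-status follow-up to patients who withdraw for any reason.
- **Section 8.2:** send deaths found this way to the Clinical Events Committee for adjudication.

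The cost is protocol and consent wording and a record search for about 12 patients, with no extra visits or procedures. Patients already consented may need IRB agreement, and the reported rate may move in either direction.
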